8.3.8 Pregnancy

All pregnancies and outcomes of pregnancy should be reported to AZ except for:

- If the pregnancy is discovered before the study participant has received any study intervention

8.3.8.1 Maternal Exposure

Women of childbearing potential are not allowed to be included in this study. Should a pregnancy still occur, the investigational product should be discontinued immediately and the pregnancy reported to AZ.

Pregnancy itself is not regarded as an adverse event unless there is a suspicion that the investigational product under study may have interfered with the effectiveness of a contraceptive medication. Congenital anomalies/birth defects and spontaneous miscarriages should be reported and handled as SAEs. Elective abortions without complications should not be handled as AEs. The outcome of all pregnancies (spontaneous miscarriage, elective termination, ectopic pregnancy, normal birth or congenital anomaly) should be followed up and documented even if the participant was discontinued from the study.

If any pregnancy occurs in the course of the study and is discovered after the first dose, then the investigator or other site personnel informs the appropriate AZ representatives within **1 day**, ie, immediately but **no later than 24 hours** of when he or she becomes aware of it.

The designated AZ representative works with the investigator to ensure that all relevant information is provided to the AZ Patient Safety data entry site **within 1 or 5 calendar days** for SAEs (see Section 8.3.7) and **within 30 days** for all other pregnancies.

The same timelines apply when outcome information is available.

The PREGREP module in the eCRF is used to report the pregnancy and the paper-based PREGOUT module is used to report the outcome of the pregnancy.

8.3.8.2 Paternal Exposure

Male participants should refrain from fathering a child or donating sperm during the study until 3 months after the final Follow-up Visit.

In case of pregnancy in the partner of a male participant, the partner's pregnancy should be reported on the pregnancy form (consent from the partner must be obtained before the pregnancy form is completed) following the same timeframe and routing as described for any participant's pregnancy. Pregnancy of the participant's partner is not considered to be an AE. These pregnancies will also be followed up, and the outcome of the pregnancy (spontaneous miscarriage, elective termination, ectopic pregnancy, normal birth or congenital anomaly) should, if possible, be obtained and documented.

8.3.9 Medication Error

If an event of medication error, drug abuse, **or** drug misuse occurs during the study, then the investigator or other site personnel informs the appropriate AZ representatives within **1 calendar day**, ie, immediately but **no later than 24 hours** of when he or she becomes aware of it.

The designated AZ representative works with the investigator to ensure that all relevant information is completed within **1** (Initial Fatal/Life-Threatening or follow up Fatal/Life-Threatening) **or 5** (other serious initial and follow up) **calendar days** if there is an SAE associated with the medication error (see Section 8.3.7) and **within 30 days** for all other medication errors.

The definition of a Medication Error can be found in Appendix B 4.

8.3.9.1 Drug Abuse

Drug abuse is the persistent or sporadic **intentional**, non-therapeutic excessive use of IMP or AstraZeneca NIMP for a perceived reward or desired non-therapeutic effect.

The full definition and examples of drug abuse can be found in Appendix B 4.

8.3.9.2 Drug Misuse

Drug misuse is the **intentional** and inappropriate use (by a study participant) of IMP or AstraZeneca NIMP for medicinal purposes outside of the authorised product information, or for unauthorised IMPs or AstraZeneca NIMPs, outside the intended use as specified in the protocol and includes deliberate administration of the product by the wrong route.

The full definition and examples of drug misuse can be found in Appendix B 4.

8.4 Overdose

For this study, any dose of investigational product greater than those specified in this protocol within the same day will be considered an overdose.

- An overdose with associated AEs is recorded as the AE diagnosis/symptoms on the relevant AE modules in the eCRF and on the Overdose eCRF module.
- An overdose without associated symptoms is only reported on the Overdose eCRF module

If an overdose on an AZ study intervention occurs in the course of the study, the investigator or other site personnel inform appropriate AZ representatives immediately, but **no later than 24 hours** of when he or she becomes aware of it.

The designated AZ representative works with the investigator to ensure that all relevant information is provided to the AZ Patient Safety data entry site **within one or 5 calendar days** for overdoses associated with an SAE (see Section 8.3.7) and **within 30 days** for all other overdoses.

8.5 Human Biological Samples

Instructions for the collection and handling of biological samples will be provided in the study specific laboratory manual. Samples should be stored in a secure storage space with adequate measures to protect confidentiality. For further details on Handling of Human Biological Samples see Appendix C.

Samples will be stored for a maximum of 15 years from the date of the issue of the CSR in line with consent and local requirements, after which they will be destroyed/repatriated.

- Pharmacokinetic samples will be disposed of after the Bioanalytical Report finalisation or 6 months after issuance of the draft Bioanalytical Report (whichever is earlier), unless consented for future analyses.
 - Pharmacokinetic samples may be disposed of or anonymised by pooling. Additional analyses may be conducted on the anonymised, pooled or individual pharmacokinetic samples to further evaluate and validate the analytical method. Any results from such analyses may be reported separately from the CSR.

8.5.1 Pharmacokinetics

Blood samples will be collected for measurement of plasma concentrations of AZD4831 as specified in the SoA (See Section 1.3). Pharmacokinetic Samples will be collected pre-dose; thus, participants should be reminded not to take their study medication at home on the day of their clinic visit as they will receive study medication in clinic on these days. Therefore, the last dose of study medication at Visit 11 for Part A, and either Visit 5, Visit 6 or Visit 7 for

Part B will be in clinic. For Part A, in a subset of participants where sites are able, additional post-dose PK samples will be collected at Visit 6 at the timepoints specified in the SoA. For participants who are discontinued from investigational product due to rash, a PK sample should be collected at the discontinuation visit. Samples may be collected at additional timepoints during the study if warranted and agreed upon between the investigator and the sponsor, eg, for safety reasons. The timing of sampling may be altered during the course of the study based on newly available data (eg, to obtain data closer to the time of peak or trough matrix concentrations) to ensure appropriate monitoring.

Plasma samples will be used to analyse the PK of AZD4831. Samples collected for analyses of AZD4831 concentration may also be used to evaluate safety or efficacy aspects related to concerns arising during or after the study.

Samples will be collected, labelled, stored, and shipped as detailed in the Laboratory Manual.

8.5.1.1 Determination of Drug Concentration

Samples for determination of drug concentration in plasma will be assayed by bioanalytical test sites operated by or on behalf of AZ, using an appropriately validated bioanalytical method. Full details of the analytical method used will be described in a separate bioanalytical report.

Drug concentration information that would unblind the study will not be reported to investigative sites or blinded personnel until the study has been unblinded.

Incurred sample reproducibility analysis, if any, will be performed alongside the bioanalysis of the test samples. The results from the evaluation, if performed, will be reported in a separate Bioanalytical Report.

Placebo samples will not be analysed unless there is a need to confirm that correct treatment has been given to study participants.

8.5.2 Pharmacodynamics

8.5.2.1 Collection of Samples

Blood samples will be collected for measurement of NT-proBNP, hsCRP, and IL-6 as specified in the SoA (See Section 1.3).

An additional 5 mL blood sample may be collected for a NT-proBNP quick test to be performed on-site for pre-screening purposes; this test will be analysed locally and will not be sent to the central laboratory. The test must be recorded by site staff on the Pre-screening Log with a date and note of potential eligibility per Inclusion Criterion 6 (See Section 5.1) as Y/N based on the test result. The pre-screening test does not replace the NT-proBNP sampling at the Screening (Visit 1) (See Section 1.3), which will be sent to the central laboratory.

Samples will be collected, handled, labelled, stored, and shipped as detailed in the Laboratory Manual.

For storage, re-use, and destruction of pharmacodynamic samples, see Section 8.5 and Appendix C.

8.6 Human Biological Sample Biomarkers

8.6.1 Collection of Blood Samples for CCI

Blood samples for exploratory quantification of CCI are required and will be collected from participants in Part A and B of this study as specified in the SoA (See Section 1.3).

Samples will be collected, handled, labelled, stored, and shipped as detailed in the Laboratory Manual. For storage, re-use and destruction of samples see Section 8.5 and Appendix C.

8.6.2 Collection of Mandatory Samples for Exploratory Biomarker and Metabolite Analysis

By consenting to participate in the study the participant consents to the mandatory research components of the study.

Blood samples for exploratory biomarker research are required and will be collected from all participants in this study as specified in the SoA (See Section 1.3). Plasma and serum samples will be collected for the analysis of biomarkers that may respond to treatment of AZD4831 and/or that may predict response to treatment with AZD4831, including but not limited to:

Category	Percentage
Other	~10%
Unknown	~10%
Developmental delay	~15%
Intellectual disability	~10%
Autism	~25%
Other developmental disorder	~10%
Other mental health condition	~5%
Other medical condition	~2%
Other physical condition	~2%

For Part A, exploratory analysis of CCI

█ will be performed at the timepoints specified in the SoA (See Section 1.3). Exploratory analysis of AZD4831 metabolites in plasma will also be performed at the timepoints specified in the SoA (See Section 1.3).

Where **CCI** is part of the parameters measured from blood samples collected for safety assessment and analysed at the central laboratory, the parameter from the sample collected for the safety assessment will be used for the exploratory biomarker analysis.

CCI will be analysed through local laboratory and entered in the appropriate eCRF page.

For Part A, for participants who discontinue investigational product due to rash or skin reaction, blood and urine will be collected at the EDV for exploratory biomarker analysis in blood and analysis of AZD4831 metabolites in urine and plasma. For Part B, only blood (plasma) will be collected for analysis of AZD4831 metabolites.

Samples will be collected, handled, labelled, stored, and shipped as detailed in the Laboratory Manual. For storage, re-use and destruction of exploratory samples, see Section 8.5 and Appendix C.

8.6.3 Collection of Mandatory Sample for Genetic Analysis

A blood sample will be collected for mandatory genetic analysis by AZ or designated organisation(s). This sample will be used to prepare DNA to assess the genotype of certain genes that may be related to how the investigational drug is metabolised by the participant's body and/or to the development of skin reactions. Genotyping will include, but will not be limited to, an assessment of the human leukocyte antigen genes. The genetic research may involve the genotyping of selected genes or the analysis of the whole genome sequence. The sample will only be used for these purposes as outlined.

The blood sample for genetic research will be obtained from the participants at Visit 3 and Visit 2 for Part A and Part B, respectively.

If for any reason the sample is not drawn at these visits, it may be taken at any visit until the last study visit. Samples will be collected, labelled, stored, and shipped as detailed in the Laboratory Manual.

8.6.4 Collection of Mandatory Samples for Potential Diagnostic Assay Development

Plasma and serum samples for potential diagnostic development are required and will be collected from all participants in Part A and B of this study as specified in the SoA (See Section 1.3). The intention of these samples is to provide additional samples for assessment of the variability in levels of candidate biomarkers that show potential to predict response to treatment with AZD4831 and to bridge from a Research Use Only assay to a diagnostic assay. The samples may be used for commercial diagnostic assay development.

Plasma and serum samples will be collected, handled, labelled, stored, and shipped as detailed in the Laboratory Manual. For storage, re-use and destruction of samples, see Section 8.5 and Appendix C.

8.6.5 Collection of Optional Samples for Future Biomarker Research

Collection of plasma, serum and urine samples for future biomarker research is also part of this study for both Part A and B as specified in the SoA (See Section 1.3) and is subject to agreement to optional consent.

Plasma, serum and urine samples will be collected for the future exploratory analysis of biomarkers that may respond to treatment with AZD4831 or that predict response to treatment with AZD4831. Distinct from the mandatory collection of exploratory samples, these samples may be used to analyse exploratory biomarkers not defined in the CSP and may include multiplex analysis using biomarker panels.

Samples will be collected, handled, labelled, stored, and shipped as detailed in the Laboratory Manual. For storage, re-use and destruction of exploratory samples, see Section 8.5 and Appendix C.

8.7 Optional Genomics Initiative Sample

Collection of optional samples for Genomics Initiative research is also part of this study as specified in the SoA (See Section 1.3) and is subject to agreement in the ICF addendum.

Blood sample for DNA isolation will be collected from participants who have consented to participate in the genetic analysis component of the study. Participation is optional.

Participants who do not wish to participate in the genetic research may still participate in the study.

See Appendix D for information regarding the Genomics Initiative genetic sample. Details on processes for collection and shipment and destruction of these samples can be found either in the appendices or in the Laboratory Manual.

For storage and destruction of genetic samples see Appendix D.

8.8 Medical Resource Utilisation and Health Economics

Medical Resource Utilisation and Health Economics parameters are not evaluated in this study.

9 STATISTICAL CONSIDERATIONS

9.1 Statistical Hypotheses

Part A – 6MWD and KCCQ-TSS change from baseline at 16 weeks:

The primary statistical test has the null hypothesis that there will be no difference between AZD4831 and placebo regarding mean change from baseline for the primary efficacy variables at 16 weeks.

$H_0: \mu(\text{AZD4831}) - \mu(\text{placebo}) = 0$, versus the alternative hypothesis:

$H_1: \mu(\text{AZD4831}) - \mu(\text{placebo}) \neq 0$, where $\mu(x)$ is true mean change from baseline for treatment x.

Part B – 6MWD change from baseline at 24 weeks:

The primary statistical test has the null hypothesis that there will be no difference between AZD4831 and placebo regarding mean change from baseline for the primary efficacy variables at 24 weeks.

$H_0: \mu(\text{AZD4831}) - \mu(\text{placebo}) = 0$, versus the alternative hypothesis:

$H_1: \mu(\text{AZD4831}) - \mu(\text{placebo}) \neq 0$, where $\mu(x)$ is true mean change from baseline for treatment x.

Part B - KCCQ-TSS change from baseline at 24 weeks:

The null hypothesis will be that neither the treatment group nor treatment-by-baseline interaction terms explain the expected change from baseline in KCCQ-TSS, ie:

$H_0: \beta_3 = \beta_4 = 0$, versus the alternative hypothesis:

$H_1: \beta_3 \neq 0$ or $\beta_4 \neq 0$ or both.

Where β_3 is the coefficient for treatment group and β_4 is the coefficient for the treatment-by-baseline interaction term. See Section 9.4.2.1 for model specification details.

9.2 Sample Size Determination

	Part A	Part B
Enrolled	Estimated 1100 participants	Estimated 1350 participants
Randomised	Estimated 660 participants	Estimated 820 participants
Participants with complete safety data	Estimated 600 participants	Estimated 745 participants

Part A

The sample size selection was based on the following assumptions:

- Change from baseline in 6MWD is approximately normally distributed with a standard deviation of 70 meters (Nassif et al 2019).
- Change from baseline in KCCQ-TSS is approximately normally distributed with a standard deviation of 18 points.

Approximately 660 participants randomised, of which we estimate approximately 600 will have complete safety data, and 1:1:1 allocation, is chosen to have enough participants exposed to AZD4831 at the therapeutic dose to fulfil the minimum requirement in the ICH E1 guideline on population exposure, taken together with Part B of this study, as well as a second function and symptom study with a similar design as Part B, and Phase 1 studies completed ahead of submission.

With 85% power at a significance level of $\alpha = 0.05$, 200 participants per arm will allow detection of a difference of 6.0 points in mean change from baseline between active and placebo in KCCQ-TSS comparing each active arm with placebo. The critical value for statistical significance is 3.9 points. The corresponding numbers for 6MWD are 21 meters and 14 meters. Calculations of detectable differences and critical values are based on ANCOVA, which will also be used for the analysis.

The potential effect of informative censoring, including all-cause mortality, will be considered during the analysis of the data and interpretation of the results, but not taken into account in the sample size calculations for Part A.

Part B

For part B, we assume that the type 1 error is controlled using Bonferroni adjustment (this is not necessarily the choice of method for type 1 error control in the analysis phase).

For KCCQ-TSS, we assume that:

- Change from baseline in KCCQ-TSS is approximately normally distributed with an expected value dependent on the baseline score, treatment group and treatment-by-baseline interaction, and with a residual error of 18.
- For KCCQ-TSS, due to the assumed treatment-by-baseline interaction, the power was assessed through simulation of normally distributed values truncated to the range [0, 100]. Simulated studies are analysed with ANCOVA with an interaction effect between treatment group and baseline KCCQ-TSS. The global null hypothesis of no impact of treatment group on the expected change from baseline is assessed by a likelihood-ratio test comparing this model to a model with no treatment effects.

Approximately 820 participants will be randomised in 1:1 allocation, of which we estimate approximately 745 will have complete safety data. The sample size is chosen to have enough participants exposed to AZD4831 at the therapeutic dose to fulfil the minimum requirement in the ICH E1 guideline on population exposure, taken together with Part A of this study as well as a second function and symptom study with a similar design as Part B, and Phase 1 studies completed ahead of submission.

With the proposed number of participants, and under the alternative hypothesis for the treatment effect represented by the line $y = 18.2 - 0.112 * \text{BASEKCCQ-TSS}$ for the difference in expected change from baseline with AZD4831 compared to placebo as a function of the baseline score, the global null hypothesis can be rejected in more than 99% of simulations.

For 6MWD, change from baseline in 6MWD is assumed to be approximately normally distributed with a standard deviation of 70 meters. Power calculations are based on a two-sample t-test with shared variance. Assuming a true difference in mean change from baseline of 19 meters, the power to reject the null hypothesis is 95% with the proposed number of participants. The critical value is 11.

9.3 Populations for Analyses

Part A

Full Analysis Set:

All participants who have been randomised to study treatment and who have received at least one dose of investigational product will be included in the Full Analysis Set irrespective of their protocol adherence and continued participation in the study. Participants will be analysed according to their randomised study medication assignment, irrespective of the treatment actually received.

Safety Analysis Set:

The Safety Analysis Set consists of all participants who have received at least one dose of investigational product. Erroneously treated participants (eg, those randomised to treatment A but actually given treatment B) are accounted for in the treatment group of the treatment they actually received. A participant who has received any dose of the experimental IP will be classified as in the experimental IP treatment group.

Part B

Full Analysis Set:

All participants who have been randomised to study treatment and who have received at least one dose of investigational product will be included in the Full Analysis Set irrespective of their protocol adherence and continued participation in the study. Participants will be analysed according to their randomised study medication assignment, irrespective of the treatment actually received.

Efficacy and safety analyses in Part B will be done on the Full Analysis Set.

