9.4.3 Safety

Safety and tolerability will be evaluated in terms of AEs, Vital signs, Clinical laboratory variables, and ECG. In addition, extra evaluation will be done for the following Adverse Events of Special Interest (AEoSI): skin reactions, including maculopapular rash, and infections (see Section 8.2). Exposure to study treatment will be described.

Safety analyses will be performed using the safety analysis set in Part A, and using the full analysis set in Part B. Safety data will be presented using descriptive statistics unless otherwise specified.

Safety analyses will be performed for two different study periods: on-study and on-treatment. These periods are defined in the Part A SAP and Part B SAP, respectively.

Safety Estimand Definition

The aim with the analyses of safety data is to assess the general safety objective, evaluated in a scenario where study treatment is not prematurely discontinued. Two analysis approaches are considered complementary to assess this hypothetical scenario for all safety endpoints:

- On-treatment; unbiased under the assumption that censoring following premature treatment discontinuation is non-informative.
- On-study; unbiased under the assumption that the risk for an event is independent of continued treatment. Note that this approach could also be described as handling premature treatment discontinuation with a treatment policy approach.

Hence, the general safety objective will be assessed through an estimand defined by the following attributes:

Population: Patients that fulfill all of the inclusion and none of the exclusion criteria..

Treatment: Treatment with either 2.5 mg or 5 mg of AZD4831 compared to placebo, administered in addition to optimal back-ground therapy for co-morbidities.

Intercurrent events:

- Premature study treatment discontinuation: All analyses will be provided using two complementary approaches.
 - Hypothetical as premature study treatment discontinuation cannot occur, implemented by excluding/censoring data after premature study treatment discontinuation + 14 days.
 - Treatment policy by ignoring study treatment discontinuation, implemented by including all available data.
- Initiation or change of concomitant medication, including rescue medication: Will be ignored, that is, handled using a treatment policy approach.

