- Death: With the exception of assessment of mortality, will be handled hypothetically as it cannot occur, implemented by censoring time to event data at death and not imputing any data after death.

Population level summaries: Distribution of endpoints by treatment group, Kaplan-Meier estimate for endpoints by treatment group, difference in Kaplan-Meier estimates between treatment groups and treatment hazard ratios.

This estimand requires that to the extent possible, randomised subjects are followed up regardless of study intervention compliance and adherence to the study protocol.

Adverse Events

All AEs will be classified by system organ class, high level group term, high level term, and preferred term according to MedDRA.

AEs will be presented for each treatment group by SOC and/or PT, covering number and percentage of subjects reporting at least one event. An overview of AEs will present for each treatment group the number and percentage of subjects with any AE, AEs with outcome of death, serious AEs, and AEs leading to discontinuation of IP. Separate AE tables will be provided taking into consideration seriousness, death, and events leading to discontinuation of IP. An additional table will present number and percentage of subjects with most common AEs. Most common (eg, frequency of $>x\%$, $\geq x\%$) will be defined in the SAP. In accordance with the requirements of the FDA, a separate table will present non-serious AEs occurring in more than 5% of subjects in any treatment group. Key subject information will be presented for subjects with AEs with outcome of death, serious AEs, and AEs leading to discontinuation of IP. An AE listing for the safety analysis set will cover details for each individual AE. AEoSIs related to skin reactions, including maculopapular rash, and infection will be presented. Full details of AE analyses will be provided in the SAP.

All safety analyses are descriptive; hence no p-values will be presented for any safety analyses, and confidence intervals are provided as an illustration of precision of the estimate. Hazard ratio between treatment groups will be based on a Cox proportional hazards regression model with a factor for treatment group.

Treatment emergent

For Part A, the definition for treatment emergent events will be provided in the SAP.

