4.6 Safety Analyses

The domain safety covers exposure, adverse events, clinical laboratory, vital signs, and electrocardiogram (ECG).

Tables, figures, and listings are provided for SAS unless otherwise stated. All tabulations of safety data (AEs, laboratory parameters, vital signs, and ECG) will be based on both the On-treatment period and On-study period respectively unless otherwise stated.

The analyses will be presented for AZD4831 2.5mg, AZD4831 5mg, AZD4831 Total (pooled treatment groups AZD4831 2.5mg and 5mg) and placebo, unless otherwise stated.

Safety estimand definition

The aim with the analyses of safety data is to assess the general safety objective; this will be done for a hypothetical scenario where study treatment is not prematurely discontinued. Two different handling of intercurrent event strategies are considered complementary to assess this hypothetical scenario for all safety endpoints:

- On-treatment; unbiased under the assumption that censoring following premature treatment discontinuation is non-informative. Note that this approach could also be described as handling premature treatment discontinuation with a hypothetical strategy.
- On-study; unbiased under the assumption that the risk for an event is independent of continued treatment. Note that this approach could also be described as handling premature treatment discontinuation with a treatment policy strategy.

Hence, the general safety objective will be assessed through two complementary estimands with respect to handling of the intercurrent event of premature discontinuation of study treatment, defined by the following attributes:

- **Population:** Subjects with an established diagnosis of HF with LVEF > 40%, as defined by the inclusion and exclusion criteria, who have received at least one dose of IP. Implemented using the safety analysis set.
- **Treatment:** Actual treatment group (i.e., not necessarily the treatment a subject was randomised to), AZD4831 2.5mg/5mg or placebo.
- **Intercurrent events:**
 - Premature study treatment discontinuation: All analyses will be provided using two complementary strategies:
 - Hypothetical strategy: Premature study treatment discontinuation cannot occur, implemented by censoring data after premature study treatment discontinuation + 14 days, using the On-treatment analysis period (Section 3.3.1.5).

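### Part B groups safety data by randomised arm with no as-treated safety set, unlike Part A, so any misdosed participant's adverse events count under a treatment they did not take; the expected effect is small and the remedy cheap

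*Protocol*

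**What the plan says.** For Part B, Protocol Section 9.3 defines one analysis set only, the Full Analysis Set: randomised participants with at least one dose. Its grouping rule is "Participants will be analysed according to their randomised study medication assignment, irrespective of the treatment actually received". The section then says "Efficacy and safety analyses in Part B will be done on the Full Analysis Set". Section 9.4.3 repeats the choice: "Safety analyses will be performed using the safety analysis set in Part A, and using the full analysis set in Part B".

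For Part A, Section 9.3 adds a Safety Analysis Set. There, participants treated in error "are accounted for in the treatment group of the treatment they actually received", and "A participant who has received any dose of the experimental IP will be classified as in the experimental IP treatment group". The Part A SAP uses this set for all safety analyses (Section 4.1.2.1) and gives the treatment attribute of its safety estimand as "Actual treatment group (i.e., not necessarily the treatment a subject was randomised to), AZD4831 2.5mg/5mg or placebo" (Section 4.6). It also lists participants who received product other than that randomised (Section 4.6.1.2) and their adverse events (Section 4.6.2.2).

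Section 9.4.3 also contains a sentence not limited to either part: "An AE listing for the safety analysis set will cover details for each individual AE". Part B has no set of that name.

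**The concern.** Safety tables are normally read as what happened to people who took each product. The aim in Section 9.4.3 points the same way: it asks about safety on AZD4831 against placebo in a setting where treatment is not stopped early. Under the Part B rule, a placebo-randomised participant who takes active drug is analysed as placebo, and an active-randomised participant who takes only placebo is analysed as active. Both errors blur the arms. For a drug that truly causes an event, that generally makes the difference look smaller, which is the unhelpful direction for detecting harm.

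Maculopapular rash is an identified risk in Table 3 and an adverse event of special interest. If it is rare on placebo, the placement of one severe case can change how the table reads. The protocol gives no reason for treating the two parts differently.

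Exposure is affected as well. Section 9.2 justifies the size of each part by the number of participants exposed to AZD4831, counted across Parts A and B toward the ICH E1 minimum. Exposure depends on drug received, which a count by randomised arm does not measure when product is mixed up.

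**Working it through.** **Does anything else in the plan correct the grouping?** The on-treatment approach in Section 9.4.3 drops or censors data from 14 days after premature discontinuation. It acts on time and never reassigns a participant by product taken. The on-study approach keeps all data and does not reassign either. So the rule in Section 9.3 decides the arm in every Part B safety table.

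**Size.** The plan states no figure on this point, so there is none to reproduce. The inputs for an illustration are:

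- Participants per arm: 820 randomised 1:1 (Section 9.2), so 820/2 = 410. As a check that the plan works with 410, take its Part B walk-distance power (difference 19 m, SD 70 m, two-sided alpha 0.025). The standard error is 70 × √(2/410) = 4.89, the critical value is 2.241 × 4.89 = 10.96 (stated: 11), and power is Φ(19/4.89 − 2.241) = 95.0% (stated: 95%).
- Rash risk on active, pA: 1/27 = 3.70% (Phase 2a study, 5 mg; Section 4.3), with 2/12 = 16.7% (Japanese and Chinese study, 5 mg; same section) as a high case.
- Rash risk on placebo, pP: not given. Assumed 0%, or 1% in the high case.
- Share of placebo participants who take active drug, m: not given. Assumed 0.25% to 5%, which is 410 × 0.0025 ≈ 1 to 410 × 0.05 ≈ 20 participants.

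Expected extra cases counted under placebo = 410 × m × (pA − pP). Observed risk difference = (1 − m) × (pA − pP). Each misdosed participant is given the full active risk, which is generous for a single wrong bottle.

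| pA, pP | m | Extra cases under placebo | Risk difference (points) |
|---|---|---|---|
| 3.70%, 0% | 0.25% | 0.04 | 3.70 → 3.69 |
| 3.70%, 0% | 5% | 0.76 | 3.70 → 3.52 |
| 16.7%, 1% | 0.25% | 0.16 | 15.67 → 15.63 |
| 16.7%, 1% | 5% | 3.2 | 15.67 → 14.88 |

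If the same share of each arm is misdosed, the factor becomes (1 − 2m). At m = 5% the first difference falls to 3.70 × 0.90 = 3.33 points and the second to 15.67 × 0.90 = 14.1.

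**One case.** At 3.7%, about 410/27 ≈ 15 rashes would occur among 410 on active. Suppose a table by treatment received shows 15 against an assumed 1, and one of the 15 was a misdosed placebo participant. By randomised arm it shows 14 against 2. With 410 as both denominators, the ratio goes from 15/1 = 15 to 14/2 = 7. To expect one such case at 3.7%, 1/0.037 = 27 placebo participants would have to take active drug, which is 27/410 = 6.6% of the arm.

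**The case against.** The best defence is that the choice looks deliberate. It is stated in two sections, and Part B safety is a comparison by time to first event with Kaplan-Meier differences and hazard ratios, for which randomised groups protect the comparison. All safety analyses are descriptive, so no power or alpha depends on it. Misdosing should be rare: kits are allocated by the IRT (Section 6.3), Part B uses one bottle rather than two (Section 6.1.1), and a second staff member confirms on-site doses (Section 6.4). A misdosed rash case could also be detected, because skin reactions trigger a visit with a PK sample (Section 8.2.5), placebo samples can be assayed to confirm correct treatment (Section 8.5.1.1), and the DMC can link treatment codes to the data (Appendix A 5).

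Most of this stands, and it limits the size of the problem. It does not change where an event is tabulated once misdosing has occurred. Detection is also not complete: Appendix B 4 exempts IRT/RTSM errors from medication-error reporting. Part B has its own SAP, which is not among the documents; it may add an as-treated analysis or a listing of misdosed participants, but the protocol promises neither.

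The listing sentence is a small matter. Both sets require a dose, so a Part B listing would contain essentially the same people.

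A reader might infer three stronger things that the documents do not support:

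- **That the rule works only against placebo.** It works in both directions.
- **That the rash ratio would be halved.** The move from 15 to 7 begins by supposing that the case occurred. The approximate 95% intervals, 2.0 to 113 for 15 against 1 and 1.6 to 31 for 14 against 2, overlap heavily.
- **That a pooled Part A and Part B safety comparison would mix two grouping rules.** Section 9.2 combines the parts only for ICH E1 exposure, and Section 4.1 bases the Part B analysis on Part B participants alone.

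**Conclusion.** The point holds as a low-impact improvement. Part B safety is grouped by randomised arm, Part A safety by treatment received, no reason is given, and one sentence in Section 9.4.3 relies on a set that Part B lacks. Without misdosing nothing changes. With an assumed 0.25% to 5% of placebo participants misdosed and rash at 3.7% on active, less than one expected case changes arm and the risk difference moves by at most 0.18 points (3.70 − 3.52). What remains is the chance that a single rare or serious event is shown under the wrong treatment.

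The misdosing share and the placebo rash rate are assumptions. The 3.7% rests on one case in 27 at 5 mg, whereas Part B may use either dose.

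**What to change.** Define a Part B Safety Analysis Set in Section 9.3 with the Part A rule: at least one dose, grouped by treatment actually received, any active dose counting as active. Use it for Part B safety and exposure tables, and change Section 9.4.3 to match. Keep the Full Analysis Set for efficacy and, if the sponsor values a randomised safety comparison, as a supportive safety analysis. Add a listing of adverse events in participants who received non-randomised product, as the Part A SAP does. Reconcile the adverse event listing sentence in Section 9.4.3 with the sets then defined.

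The cost is wording in two sections, one derived variable and one listing, best settled before unblinding. The downside is that a placebo participant with a single active dose counts as active throughout, for up to 48 weeks of events. Part A already accepts this, and a supportive analysis by randomised arm would show whether it matters.
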